10.3. Risk-Benefit Rationale

Access to automated insulin devices during the trial may offer improved glycemic control for participants, and may increase understanding of the disorder, due to the fact that the participants will be followed with higher frequency of visits, which will allow a closer medical follow-up when compared to standard of care.

Previous studies have demonstrated safety and efficacy of the MiniMed 670G system in the pivotal study (Garg, 2017) and in real-life settings (Agrawal, 2018). It is anticipated that with the newer iterations of the investigated AHCL algorithm maximize time spent in hybrid closed-loop operation, relative to the current commercialized MiniMed™ 670G system, which will further improve glucose control, time in glycemic range and overall user satisfaction.

The current commercialized MiniMed™ 670G system and advanced algorithm involve periodic automated insulin dosing, that may increase the likelihood of hypoglycemia, and periodic automated attenuation of

insulin delivery, that may increase the likelihood of hyperglycemia. However, the number of Serious Adverse Events that occurred in past studies involving the commercialized MiniMed™ 670G system (Bergenstal, 2016) were relatively rare, and none occurred during the feasibility studies with new AHCL MiniMed™ 670G, version 4.0.

Furthermore, with any externally worn device there are small risks of insulin infusion site reactions, infection, and skin reactions to tapes – however it should be noted that this is no different to standard of care insulin pump therapy and utilizing continuous glucose monitoring. Also, one goal of the run-in phase is to identify patients who do not tolerate sensor wear and therefore, they would not be eligible to be randomized into the study.

In addition, any potential risks with this study are minimized by selecting qualified investigators experienced with insulin pump therapy, careful assessment of each subject during the study conduct to effectively monitor and rapidly remedy the problem. Furthermore, subjects can call the local support line to obtain technical support, if needed.

Medtronic has further minimized the possibility of risks by completing product testing prior to the use of the system in this clinical study, implementing quality control measures into production processes, providing guidelines for subject selection and evaluation, and providing adequate instructions and labelling according to local requirements.

All above these risks are contained within the patient information sheet, and indications and contraindications are provided in the Instructions for Use given to all patients.

Finally, in the context of pandemic, the risk of visiting the site for the subject has been mitigated via the setup of remote visits.

11. Adverse Events and Device Deficiencies

11.1. Adverse Events

Throughout the course of the study, investigational centers will make all efforts to remain alert to possible reportable adverse events (AEs) or untoward findings. All adverse events identified from the point of enrollment until the subject's exit from the study will be reported to the sponsor and documented on the Adverse Event eCRF and in the subject's medical records. The study personnel will elicit reports of adverse events (AEs) from the subject at each visit (including phone calls) documenting the medical diagnosis, date of event start and end, causality (relationship to device or procedure), treatment, outcome, and description that includes the details of the event.

11.2. Definitions and Classification

Medtronic uses the definitions provided in ISO 14155:2020 for AE definitions.

Where the definition indicates "device", it refers to any device used in the study. This might be the device under investigation, or any market released component of the system. Medtronic follows MEDDEV 2.7/3 revision 3 (or subsequent versions) guidelines for classifying causality levels; but will apply these causality definitions across all events, not only serious adverse events and definitions have been adapted accordingly.

Severe Hypoglycemia is an event requiring assistance of another person due to altered consciousness to actively administer carbohydrate, glucagon, or other resuscitative actions. This means that the subject was impaired cognitively to the point that he/she was unable to treat his or her self, was unable to verbalize his or her needs, and was incoherent, disoriented and/or combative.

These episodes may be associated with sufficient neuroglycopenia to induce seizure or coma. Plasma glucose measurements may not be available during such an event, but neurological recovery attributable to the restoration of plasma glucose to normal is considered sufficient evidence that the event was induced by a low plasma glucose concentration. (*Adapted from American Diabetes Association Workgroup on Hypoglycemia, Diabetes Care 28:1245-1249, 2005*)

Severe Hyperglycemia is defined as hyperglycemia (blood glucose greater than >300 mg/dL (16.7 mmol/L) with blood glucose ketones greater than > 0.6 mmol/L or accompanied by symptoms of nausea, vomiting or abdominal pain.

Diabetic Ketoacidosis/DKA diagnostic criteria: blood glucose greater than > 250 mg/dL (or greater than > 13.9 mmol/L), arterial pH less than < 7.3 , bicarbonate less than < 15 mEq/L, moderate ketonuria or ketonemia and requiring treatment within a health care facility. (*American Diabetes Association-Diabetes Care, Volume 27, Supplement 1, January 2004; S94-S102*)

Hyperglycemic events will be recorded as DKA if the event includes the presence of all of the following:

- Arterial blood pH less than < 7.30 or serum bicarbonate less than < 15 mEq/L
- Blood glucose greater than > 250 mg/dL (or greater than > 13.9 mmol/L)
- Serum ketones or large/moderate urine ketones
- Symptoms such as polyuria, polydipsia, nausea, or vomiting
- Treatment provided in a health care facility

Adverse Event (AE): (ISO 14155:2020, 3.2)

Any untoward medical occurrence, unintended disease or injury, or untoward clinical signs (including abnormal laboratory findings) in subjects, users or other persons, whether or not related to the investigational medical device and whether anticipated or unanticipated.

NOTE 1: This definition includes events related to the investigational medical device or the comparator.

NOTE 2: This definition includes events related to the procedures involved.

NOTE 3: For users or other persons, this definition is restricted to events related to investigational medical devices or comparators.

Adverse Device Effect (ADE): (ISO 14155:2020, 3.1)

Adverse event related to the use of an investigational medical device

NOTE 1: This definition includes AEs resulting from insufficient or inadequate instructions for use, deployment, implantation, installation, or operation, or any malfunction of the investigational medical device.

NOTE 2: This definition includes any event resulting from an error use or from intentional misuse of the investigational medical device.

NOTE 3: this includes 'comparator' if the comparator is a medical device.

Serious Adverse Event (SAE): (ISO 14155:2020, 3.45)

Adverse event that led to any of the following

- a) death,
- b) serious deterioration in the health of the subject, users or other persons as defined by one or more of the following:
 - 1) a life-threatening illness or injury, or
 - 2) a permanent impairment of a body structure or a body function, including chronic disease, or
 - 3) in-patient or prolonged hospitalization, or
 - 4) medical or surgical intervention to prevent life-threatening illness or injury or permanent impairment to a body structure or a body function,
- c) fetal distress, fetal death or a congenital abnormality or birth defect including physical or mental impairment

NOTE 1: Planned hospitalization for a pre-existing condition, or a procedure required by the CIP, without serious deterioration in health, is not considered a *serious adverse event*.

For the purpose of this study, the term "life-threatening" in the definition of "serious" refers to an event in which the patient was at risk of death at the time of the event; it does not refer to an event which hypothetically might have caused death if it were more severe. (ICH Topic E 2 A Clinical Safety Data Management: Definitions & Standards for Expedited Reporting. EMEA 2006)

Definition for Germany only: **Serious Adverse Event (SAE):** (*MPSV § 2 Definition Abs 5*)

A serious adverse event is an event that occurs in a clinical investigation subject to approval or occurring in a performance evaluation which led, might have led or could lead directly or indirectly to death or serious deterioration of health of the subject, the user or a third party, without consideration if the event has been caused by the medical device itself; this applies accordingly to serious adverse events occurring in a clinical investigation or performance evaluation for which an exemption of the approval authorization as per MPG § 20 paragraph 1 sentence 2 has been granted.

Serious Adverse Device Effect (SADE): (*ISO 14155:2020, 3.44*)

Adverse device effect that has resulted in any of the consequences characteristic of a serious adverse event.

Unanticipated Serious Adverse Device Effect (USADE): (*ISO 14155:2020, 3.51*)

Serious adverse device effect which by its nature, incidence, severity or outcome has not been identified in the current risk assessment

NOTE 1: ASADE is an effect which by its nature, incidence, severity or outcome has been identified in the risk assessment.

Serious Health Threat (*ISO 14155:2020, 3.46*)

Signal from any adverse event or device deficiency that indicates an imminent risk of death or a serious deterioration in the health in subjects, users or other persons, and that requires prompt remedial action for other subjects, users or other persons

NOTE 1: This would include events that are of significant and unexpected nature such that they become alarming as a potential serious health hazard or possibility of multiple deaths occurring at short intervals.

Device deficiency: (*ISO 14155:2020, 3.19*)

Inadequacy of a medical device with respect to its identity, quality, durability, reliability, usability, safety or performance.

NOTE 1: DD include malfunctions, use errors and inadequacy in the information supplied by the manufacturer including labeling.

NOTE2: This definition includes device deficiencies related to the investigational medical device or the comparator.

Relatedness:

Device Related: An AE that results from the presence or performance (intended or otherwise) of the device.

Procedure Related: An AE that occurs due to any study procedure (ie. Blood draw).

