FLAIR Study	12 weeks, randomized vs 670G, two-sequence crossover multi-center study in 112 subjects 14-30 years old with Type 1 Diabetes in United States, Germany, Slovenia and Israel	Efficacy and Safety, Time in Hyperglycemia >10 mmol/L and Time in Hypoglycemia 3.0 mmol/L	Completed 2020
Medtronic ADAPT study	2 weeks run-in + 6-month randomized phase AHCL vs MDI, single crossover + 6-month continuation AHCL with 124 subjects > 18 years old with Type 1 Diabetes in France, UK and Germany	Efficacy and Safety, HbA1c	Expected completion 2021

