5.3.2.1. Safety Endpoint

- Number of severe hypoglycemic events
- Number of DKA events
- Number of Serious Adverse Events (SAE)
- Number of Serious Adverse Device Effects (SADE)
- Number of Unanticipated Serious Adverse Device Effects (USADE)
- Number of Device deficiencies

The above endpoints will also be assessed in Cohort B in an exploratory manner, as well as the difference in the mean HbA1c change (6 months - baseline) between the AHCL and the MDI + RT-CGM arms.

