11.3.2. Reporting of Device Deficiencies

Device Deficiency information will be collected throughout the study and reported to Medtronic, via the electronic CRF. Vigilance reporting will be done for CE-Marked devices, according to these CRF reported data.

All Device Deficiencies that did not lead to an Adverse Event should be reported on the Device Deficiency eCRF, one for each Device Deficiency, completing as much information as is available. This Device Deficiency eCRF must be validated / saved “complete” for submission to Medtronic.

See the Device Deficiency eCRF for the information to be reported for each Device Deficiency that did not lead to an Adverse Event.

Device deficiencies that did not lead to an Adverse Event, but could have led to a SADE:

- a) if either suitable action had not been taken,
- b) if intervention had not been made, or
- c) if circumstances had been less fortunate

also defined as Device Deficiencies with SADE potential require immediate reporting to the sponsor via completion of the applicable CRF, to IRB/EC and to regulatory authority per local reporting requirements ISO14155:2020 (Refer to Table 8). For Germany, refer to German Local Amendment A, or subsequent versions, for more details.

All Device deficiencies will be reported to Investigators, Regulatory Authorities and IRB/IEC as part of the Study report(s).

In case technical issue occurs with the electronic CRF (i.e. Internet access, system maintenance...), initial reporting for Device Deficiencies that require immediate reporting (see Table 7), may be done via email: [contact]. In the event the internet is not functioning, the site will inform Medtronic Study Manager via phone (see Sponsor list for contact details).

The site should contact their local clinical referent or the study manager in case of questions. Contact details are given in the Sponsor List.

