7.10.2 Number of diabetic ketoacidosis events

A diabetic ketoacidosis event is defined as an event of blood glucose greater than 250 mg/dL(13.9 mmol/L) arterial pH less than 7.3, bicarbonate less than 15mEq/l, moderate ketonuria or ketonemia, and requiring treatment within a health care facility.

Total number of diabetic ketoacidosis events will be reported continuation phase categorized by study arm. The number of diabetic ketoacidosis events per 100 patients' year during the study phase will be calculated in a similar way as in section 7.10.1 and will be reported by periods.

7.10.3 Number of Serious Adverse Events, Serious Adverse Device Effects, Unanticipated Serious Adverse Device Effects and Device Deficiencies

Serious Adverse Event (SAE) is adverse event that led to any of the following:

- a) death,
- b) serious deterioration in the health of the subject, users or other persons as defined by one or more of the following:
 - 1. a life-threatening illness or injury, or
 - 2. a permanent impairment of a body structure or a body function, including chronic disease, or
 - 3. in-patient or prolonged hospitalization, or
 - 4. medical or surgical intervention to prevent life-threatening illness or injury or permanent impairment to a body structure or a body function,
- c) fetal distress, fetal death or a congenital abnormality or birth defect including physical or mental impairment.

NOTE 1: Planned hospitalization for a pre-existing condition, or a procedure required by the CIP, without serious deterioration in health, is not considered a serious adverse event.

For the purpose of this study, the term "life-threatening" in the definition of "serious" refers to an event in which the patient was at risk of death at the time of the event; it does not refer to an event which hypothetically might have caused death if it were more severe.

Serious Adverse Device Effect (SADE) is adverse device effect that has resulted in any of the consequences characteristic of a serious adverse event. Unanticipated Serious Adverse Device Effect (USADE) is serious adverse device effect which by its nature, incidence, severity or outcome has not been identified in the current risk assessment.

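### The SAE count can mix two definitions: Germany's includes potential harm, and no step restores the ISO definition before the events are pooled

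*Protocol*

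**What the plan says.** Protocol 11.2 first adopts ISO 14155:2020 for adverse event definitions. Under it, an SAE is an "Adverse event that led to any of the following": death, serious deterioration in health, or fetal harm. A note on the term life-threatening adds that "it does not refer to an event which hypothetically might have caused death if it were more severe".

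The same section then gives a second SAE definition, labelled "Definition for Germany only" and attributed to the German ordinance. It covers an event "which led, might have led or could lead directly or indirectly to death or serious deterioration of health of the subject", or of a user or third party. It stands among the definitions, and its wording does not confine it to expedited reporting.

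Protocol 5.3.2.1 lists the SAE count as a safety endpoint, without saying which definition governs it. Table 1 in protocol 4.1 describes this study as enrolling subjects with "Type 1 Diabetes in France, UK and Germany".

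SAP 7.10.3 gives only the ISO wording: "Serious Adverse Event (SAE) is adverse event that led to any of the following". It reports the counts by study arm and asks for a listing. It has no split by country, and SAP 7.3 pools the centres.

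**The concern.** An investigator assesses seriousness for every adverse event (protocol 11.3.1) and enters it on one common form. At a German site, the protocol's own rule makes some events serious that the SAP's definition would not count.

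The documents supply a realistic example. Severe hyperglycemia (glucose above 300 mg/dL with ketones above 0.6 mmol/L, or with symptoms) is a reportable adverse event. An episode that resolves at home, with no listed consequence, can be non-serious under ISO. Protocol 10.1.1 names ketoacidosis, shock and coma among the risks of hyperglycemia, so a German investigator could classify the same episode as an SAE because of what it could lead to.

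At stake are the meaning of the SAE total, its comparability across countries and with studies that use the ISO definition, and the figures before the data monitoring committee, which monitors adverse events and advises on continuing the trial (protocol 12.2). About 70 + 34 = 104 subjects are to be randomized, so a few reclassified events could visibly change the totals.

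**Working it through.** The plan states no SAE rate, so there is no figure to reproduce. The check has three parts.

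**1. The definitions side by side**

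| Source | Harm that occurred | Potential harm |
|---|---|---|
| Protocol 11.2, ISO | yes | no, apart from item b)4, which counts an intervention given to prevent serious harm |
| Protocol 11.2, Germany | yes | yes |
| SAP 7.10.3 | yes | as ISO |

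The German set is therefore wider than the set that the SAP defines.

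**2. Is there a step that reconciles them?**

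- Clinical events committee (protocol 12.1): it agrees or disagrees with the investigator on seriousness. The definition it applies is not stated, nor whether its view replaces the site's in the count.
- German Local Amendment A: cited in protocol 11.3 and 11.3.2, in both places for reporting.
- SAP 7.3 and 7.10.3: pooling and tabulation by arm, with no derivation from site-reported to ISO SAEs.

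None of these re-classifies a German-only SAE before it is counted.

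**3. Size, on assumed inputs**

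Let g be the German share of ISO-type SAEs, and r the ratio of German-definition to ISO SAEs at German sites. Set the ISO-only total to 1. The other countries contribute 1 − g and Germany contributes gr, so

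factor = (1 − g) + gr = 1 + g(r − 1).

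The documents give neither g nor r. The share g equals the German share of follow-up only if ISO SAE rates are the same in every country.

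| | r = 1 | r = 1.5 | r = 2 | r = 3 |
|---|---|---|---|---|
| g = 0.10 | 1.00 | 1.05 | 1.10 | 1.20 |
| g = 1/3 | 1.00 | 1.17 | 1.33 | 1.67 |
| g = 0.60 | 1.00 | 1.30 | 1.60 | 2.20 |

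For example, with g = 1/3 and r = 2: 1 + (1/3)(2 − 1) = 1.33.

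For the arm contrast, suppose ISO SAEs are equal in the two arms (1 per arm). Let e = g(r − 1) be the extra German-only events in the control arm, with r taken in that arm, and let q be the AHCL-to-control ratio of those extra events. Then

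pooled arm ratio = (1 + qe)/(1 + e).

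- q = 1: the ratio is 1.00 for any e.
- q = 2, e = 0.10 × 0.5 = 0.05: 1.10/1.05 = 1.05.
- q = 2, e = (1/3) × 1 = 0.33: 1.67/1.33 = 1.25.
- q = 2, e = 0.60 × 2 = 1.20: 3.40/2.20 = 1.55.

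The contrast moves only when q differs from 1, and the documents give no value for q.

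**The case against.** The best defence is that the SAP already settles the matter. It counts SAEs under the ISO wording, the protocol adopts ISO at the head of 11.2, and the German text is a labelled national exception whose natural home is reporting to the authority. The committee reviews seriousness, SAP 7.10.3 requires a listing, and protocol 13.6 claims no significance for safety tests. The German amendment is not among the supplied documents and might contain the missing rule. The supplied SAP is written for the continuation phase, when every subject uses AHCL, although 7.10.3 itself refers to run-in and study phase, a mismatch that also needs reconciling.

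Much of this stands. Mixed counting is inferred from the absence of a rule; neither document states it. ISO may well be the intended counting rule, but an intention does not re-classify an event that a German site has recorded as serious, and no step does so.

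Four stronger readings are tempting and are not supported:

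- **Serious adverse device effects are inflated too.** They have one definition, with no German variant, and it requires a serious consequence to have resulted.
- **Harmless deficiencies are counted twice only in Germany.** SAP 7.10.3 reports both all deficiencies and those with serious potential, so one occurrence can fall under both in any country. Protocol 11.3.2 sends deficiencies without an adverse event to their own form and deals separately with "Device deficiencies that did not lead to an Adverse Event, but could have led to a SADE".
- **The AHCL arm will look worse.** Protocol 10.1.1 lists infusion-set occlusion as a pump risk, so a difference is possible, but no near-miss rates by arm are given. Allocation is 1:1 in country-level blocks (protocol 9.10), and the event definitions also cover the comparator.
- **Other sites count only harm that happened.** Item b)4 already includes preventive intervention.

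**Conclusion.** The point holds as a gap in the definition of the endpoint. A rule stated in the protocol lets German sites record SAEs that the SAP's definition excludes, and nothing brings those events back to ISO before they are pooled. The SAE total can therefore depend on the German share of events. The conclusion needs no assumed number.

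The size does. It is 1 + g(r − 1) with both inputs assumed: nothing at r = 1, and +5% to +120% over g = 0.10 to 0.60 and r = 1.5 to 3. These figures illustrate sensitivity and do not estimate the effect. Both arms face the same mix of definitions, so bias in the arm contrast cannot be inferred unless near-miss events differ by arm. The primary HbA1c analysis is untouched and the safety comparisons are exploratory, so this is worth correcting but does not threaten the trial's main conclusion.

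**What to change.** - In protocol 5.3.2.1, state that the SAE endpoint counts, in every country, only events that meet ISO 14155:2020 criteria a) to c).
- On the adverse event form, record which seriousness criterion was met, with an option for events serious only under the German definition.
- In protocol 12.1, have the clinical events committee confirm seriousness under ISO, and say that this result feeds the count.
- In SAP 7.10.3, show SAEs that qualify only under the German definition on a separate line and in a separate listing.
- Leave German regulatory reporting unchanged.

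The cost is a wording change in both documents, one extra data field and one extra table line. The committee already reviews seriousness, so its added work is small. Events already recorded at German sites would need the criterion filled in retrospectively.
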